2. LIST OF ABBREVIATIONS

Term	Definition / description
AE	Adverse Event
AESI	Adverse event of special interest
ALT	Alanine aminotransferase
AST	Aspartate aminotransferase
AUC _{0-∞}	Area under the concentration-time curve of the analyte in serum over the time interval from 0 extrapolated to infinity
AUC _{0-tz}	Area under the concentration-time curve of the analyte in serum over the time interval from 0 to the last quantifiable data point
BI	Boehringer Ingelheim
C _{max}	Maximum measured concentration of the analyte in serum
COVID	Coronavirus disease
CTP	Clinical Trial Protocol
CTR	Clinical Trial Report
CV	Arithmetic coefficient of variation
ECG	Electrocardiogram
gCV	geometric coefficient of variation
gMean	Geometric mean
ICH	International Conference On Harmonisation
IPD	Important protocol deviations
MedDRA	Medical Dictionary For Regulatory Activities

PK	Pharmacokinetics
PKS	Pharmacokinetic parameter analysis set
RAGe	Report appendix generator
RPM	Report Planning Meeting
SAE	Serious adverse event
SD	Standard Deviation
SOC	System Organ Class
TS	Treated set
TSAP	Trial Statistical Analysis Plan

Term	Definition / description
ULN	Upper limit of normal range

3. INTRODUCTION

As per ICH E9 ([1](#)) the purpose of this document is to provide a more technical and detailed elaboration of the principal features of the analysis described in the revised CTP, and to include detailed procedures for executing the statistical analysis of the primary variables and other data.

This TSAP assumes familiarity with the CTP and its amendments. In particular, the TSAP is based on the planned analysis specification as written in CTP Section 7 "Statistical Methods and Determination of Sample Size". Therefore, TSAP readers may consult the revised CTP for more background information on the study, e.g., on study objectives, study design and population, treatments, definition of measurements and variables, planning of sample size, randomisation.

Study data as collected in the eCRF will be stored in a trial database within the RAVE EDC system. All study data also including external data will then be uploaded to the CDR data warehouse.

The statistical analyses will be performed within the validated working environment CARE, including SASTM (current Version 9.4, by [REDACTED]), and a number of SASTM-based tools (e.g., macros for the analyses of AE data or laboratory data; Report Appendix Generator system (RAGe) for compilation/formatting of the CTR appendices).

PK parameters will be calculated using Phoenix WinNonlinTM software (version Phoenix 8.1, [REDACTED]).

4. CHANGES IN THE PLANNED ANALYSIS OF THE STUDY

All analyses described in this TSAP are in accordance with the statistical methods described in the revised CTP.

In this trial, PK [REDACTED] are measured in serum. However, at some places in the CTP ‘plasma’ was written where actually it should be ‘serum’, e.g. in the definition of PK endpoints.

In this TSAP these passages were corrected, i.e. ‘plasma’ was replaced by ‘serum’.

5. ENDPOINTS

5.1 PRIMARY ENDPOINT

Primary endpoints are PK endpoints of BI 765080, as defined in Section 2.1.2. of the **CTP**:

- *AUC_{0-t_z} (area under the concentration-time curve of the analyte in serum over the time interval from 0 to the last quantifiable data point)*
- *C_{max} (maximum measured concentration of the analyte in serum)*

5.2 SECONDARY ENDPOINTS

5.2.1 Key secondary endpoints

Not applicable.

5.2.2 Secondary endpoints

Secondary PK endpoint of BI 765080, is as defined in Section 2.1.3 of the **CTP**:

- *AUC_{0-∞} (area under the concentration-time curve of the analyte in serum over the time interval from 0 extrapolated to infinity)*

Secondary endpoint for assessment of safety and tolerability of BI 765080 is the occurrence (absolute number and percentage) of drug-related adverse events.

5.3.1 Safety parameters

Safety and tolerability of BI 765080 will be assessed based on further safety parameters defined in Section 2.2.2.2 of the **CTP**:

- *AEs (including clinically relevant findings from the physical examination)*
- *Safety laboratory tests*
- *12-lead ECG*
- *Vital signs (blood pressure, pulse rate)*

6. GENERAL ANALYSIS DEFINITIONS

6.1 TREATMENTS

For basic study information on treatments to be administered, assignment of treatment groups, and selection of doses, cf. Section 4 of the CTP.

Subjects will receive 100 mg BI 765080 either as

- subcutaneous injection as bolus (Test Treatment T)

or as

- 30 minute intravenous infusion (Reference Treatment R)

For statistical analysis of AEs, the following analysis phases are defined for each subject.

Table 6.1: 1 Analysis phases for statistical analysis of AEs, and actual treatment for analysis of laboratory data and vital signs

Study analysis phase	Label	Start	End
Screening ¹	Screening	Date of informed consent	Date/time of start of administration of study drug
On-treatment	BI SC or BI IV	Date/time of start of administration of study drug	12:00 a.m. on day after last contact date

¹ See [Section 6.7](#) for definition of baseline, which will be used in the statistical analyses of safety laboratory data, ECG and vital signs.

AE summary tables will present results for the on-treatment phase only. All AEs will be listed.

In AE tables in CTR Section 15.3 (but not in Appendix 16.1.13.1.8.1), the following total will be provided in addition:

- "Total", defined as the total over on-treatment phases BI injection and BI infusion

Safety laboratory data, vital signs and PK [REDACTED] parameters will be analysed based on treatment groups with clear differentiation between baseline (cf. [Section 6.7](#)) and on-treatment measurements. Measurements will be considered on-treatment, if they were taken within the on-treatment phases as defined in Table 6.1: 1.

More details on the technical implementation of these analyses are provided in the ADS Plan of this TSAP.

6.2 IMPORTANT PROTOCOL DEVIATIONS

Consistency check listings (for identification of deviations from time windows) and a list of protocol deviations (e.g. deviations in drug administration, in blood sampling times, etc.) will be provided to be discussed at the Report Planning Meeting. At this meeting, it will be decided whether a discrepant data value can be used in analyses or whether it must be corrected in the clinical database. Each protocol deviation must be assessed to determine whether it is an important PD (IPD). For definition of IPDs, and for the process of identification of these, refer to the BI reference document "Identify and Manage Important Protocol Deviations (IPD)" (2) and the DV domain template.

If any IPDs are identified, they are to be summarised into categories and will be captured in the decision log. Categories which are considered to be IPDs in this trial are defined in the DV domain template. If the data show other IPDs, the definition in the DV domain template will be supplemented accordingly by the time of the Report Planning Meeting.

IPDs will be summarized and listed. Which kind of IPDs could potentially lead to exclusion from which analysis set is specified in the DV domain template. The decision on exclusion of subjects from analysis sets will be made at the latest at the Report Planning Meeting, after discussion of exceptional cases and implications for analyses.

Non-important COVID-19 related PDs will also be summarised and listed.

6.3 SUBJECT SETS ANALYSED

The treated set (TS) and pharmacokinetic parameter analysis set (PKS) will be used as defined in the CTP, Section 7.3.

[figure not shown]

Table 6.3: 1 Subject sets analyzed

Class of endpoint	Subject set	
	TS	PKS
Disposition	X	
iPDs	X	
Primary PK endpoints		X
Secondary PK endpoint		X
Secondary Safety endpoint	X	
[REDACTED]		
Safety parameters	X	
Local tolerability	X	
Demographic/baseline characteristics	X	
[REDACTED]		

6.5 POOLING OF CENTRES

This section is not applicable, because the study was performed in only one centre.

6.6 HANDLING OF MISSING DATA AND OUTLIERS

CTP: “*If a subject is removed from or withdraws from the trial prior to the administration of trial medication, the data of this subject will not be entered in the case report form (CRF) and will not be reported in the clinical trial report (CTR). If a subject is removed or withdraws from the trial after the administration of trial medication, this will be documented and the reason for discontinuation must be recorded in the CRF. In addition, the data will be included in the CRF and will be reported in the CTR.*”

CTP: “*It is not planned to impute missing values for safety parameters.*”

One exception where imputation might be necessary for safety evaluation is AE dates. Missing or incomplete AE dates are imputed according to BI standards (3).

Missing data and outliers of PK [REDACTED] data are handled according to BI standards (4) and (5).

CTP: “*Pharmacokinetic parameters that cannot be reasonably calculated based on the available drug concentration-time data will not be imputed.*”

6.7 BASELINE, TIME WINDOWS AND CALCULATED VISITS

In all analyses, baseline is defined as the last available value prior to start of infusion/injection.

7. PLANNED ANALYSIS

The format of the listings and tables will follow the BI guideline "Reporting of clinical trials and project summaries" (6).

The individual values of all subjects will be listed. Listings will be sorted by treatment, subject number and visit (if visit is applicable in the respective listing). AE listings will be sorted by assigned treatment (see [Section 7.8.1](#) below for details). The listings will be contained in Appendix 16.2 (SDL) of the CTR.

The following standard descriptive statistical parameters will be displayed in summary tables of continuous variables:

N	number of non-missing observations
Mean	arithmetic mean
SD	standard deviation
Min	minimum
Median	median
Max	maximum

For serum concentrations as well as for all PK parameters the following descriptive statistics will additionally be calculated:

CV	arithmetic coefficient of variation
gMean	geometric mean
gCV	geometric coefficient of variation

For PK parameters the following descriptive statistics will additionally be calculated:

P10	10 th percentile
Q1	1 st quartile
Q3	3 rd quartile
P90	90 th percentile

The data format for descriptive statistics of serum concentrations will be identical with the data format of the respective concentrations. The descriptive statistics of PK parameters will be calculated using the individual values with the number of decimal places as provided by the evaluation program. Then the individual values as well as the descriptive statistics will be reported with three significant digits in the CTR.

Tabulations of frequencies for categorical data will include all possible categories and will display the number of observations in a category as well as the percentage (%) relative to the respective treatment group. Percentages will be rounded to one decimal place. The category missing will be displayed if and only if there actually are missing values. Percentages will be based on all subjects in the respective subject set whether they have non-missing values or not.

7.1 DEMOGRAPHIC AND OTHER BASELINE CHARACTERISTICS

Only descriptive statistics are planned for this section of the CTR. These will be based on the TS.

7.2 CONCOMITANT DISEASES AND MEDICATION

Concomitant diseases will be coded according to the most recent version of MedDRA. Concomitant medication will be coded according to the most recent version of the World Health Organisation – Drug Dictionary. Concomitant non-drug therapies will be coded according to the most recent version of MedDRA.

Only descriptive statistics are planned for this section of the CTR.

CTP: *Previous and concomitant therapies will be presented per treatment group without consideration of time intervals and treatment periods.*

A medication will be considered concomitant to study drug, if it

- is ongoing at the time of study drug administration, or
- starts within the analysis phase of the respective treatment (see [Section 6.1](#) for a definition of analysis phases).

The relevance of the concomitant therapies to the evaluation of PK will be decided no later than at the RPM.

7.3 TREATMENT COMPLIANCE

Treatment compliance will not be analyzed as a specific endpoint. Any deviations from complete intake will be addressed in the Report Planning Meeting (cf. [Section 6.2](#)) and described in the CTR.

7.4 PRIMARY ENDPOINTS

7.4.1 Primary analysis of the primary endpoints

The analysis of primary endpoints will be based on the PKS.

CTP: *The statistical model used for the analysis of the primary endpoints will be an analysis of variance (ANOVA) model on the logarithmic scale. That is, the PK endpoints will be log-transformed (natural logarithm) prior to fitting the ANOVA model. This model will include effects accounting for the following source of variation: treatment and matching pair. The effect of treatment will be considered as fixed. For each matched pair in the study a pair number will be assigned for analysis purpose. The resulting variable 'matched pair' will be considered as random effect. The model is described by the following equation:*

$$y_{km} = \mu + \tau_k + s_m + e_{km}, \text{ where}$$
$$y_{km} = \text{logarithm of response measured on subject } m \text{ receiving treatment } k$$

μ = the overall mean,
 τ_k = the k^{th} treatment effect, $k = 1, 2,$
 s_m = the effect associated with the m^{th} matching pair, $m = 1, 2, \dots, 14,$
 e_{km} = the random error associated with the m^{th} subject who received treatment $k.$
where $s \sim N(0, \sigma_B^2)$ i.i.d., $e \sim N(0, \sigma_w^2)$ i.i.d., σ_w^2 and s_m, e_{km} are independent random variables.

Point estimates for the ratios of the geometric means (test/reference) for the primary endpoints (see Section 2.1) and their two-sided 90% confidence intervals (CIs) will be provided.

For each endpoint, the difference between the expected means for log(T)-log(R) will be estimated by the difference in the corresponding adjusted means (Least Squares Means). Additionally their two-sided 90% confidence intervals will be calculated based on the residual error from the ANOVA and quantiles from the t-distribution. These quantities will then be back-transformed to the original scale to provide the point estimate and 90% CIs for each endpoint.

Exclusion of PK parameters

[figure not shown]
The ADS ADPP contains column variables APEXC and APEXCO indicating inclusion/exclusion (APEXC) of a PK parameter and an analysis flag comment (APEXCO). All analyses based on the PKS are based on PK parameter values which are not flagged for exclusion, i.e. with APEXC equal to "Included".

CTP: Serum concentration data and parameters of a subject which is flagged for exclusion will be reported with its individual values but will not be included in the statistical analyses.

Exclusion of serum/urine concentrations

The ADS ADPC (PK concentrations per time-point or per time-interval) contains column variables ACEXC or ACEXCO indicating inclusion/exclusion (ACEXC) of a concentration and an analysis flag comment (ACEXCO). Exclusion of a concentration depends on the analysis flag comment ACEXCO. For example, if ACEXCO is set to "ALL CALC", the value will be excluded for all types of analyses based on concentrations. If ACEXCO is set to "DESC STATS" the value will be excluded from descriptive evaluations per planned time point/time interval. If ACEXCO contains the addition "TIME VIOLATION" or "TIME DEVIATION", the value can be used for further analyses based on actual times. If ACEXCO is set to "HALF LIFE", the value will be excluded from half-life calculation only; the value is included for all other analyses. Excluded concentration itself will be listed in the CTR associated with an appropriate flag.

Further details are given in "Noncompartmental Pharmacokinetic/ Pharmacodynamic Analyses of Clinical Studies [\(4\)](#) and "Description of Analytical Transfer Files and PK/PD Data Files" [\(5\)](#).

7.5 SECONDARY ENDPOINTS

7.5.1 Key secondary endpoints

This section is not applicable as no key secondary endpoint has been specified in the protocol.

7.5.2 Secondary endpoints

7.5.2.1 Secondary endpoint analysis

[figure not shown]
CTP: *The secondary PK endpoints (refer to Section 2.1.3) will be calculated according to the BI SOP 'Standards and processes for analyses performed within Clinical Pharmacokinetics/Pharmacodynamics' and will be assessed statistically using the same methods as described for the primary endpoints.*

[figure not shown]
Drug-related adverse event will be presented descriptively by treatment group.

7.6.1 Safety parameters

Safety endpoints and tolerability will be analysed as described in [Section 7.8](#) of this TSAP.

7.7 EXTENT OF EXPOSURE

Only listings are planned for this section of the report.

7.8 SAFETY ANALYSIS

All safety analyses will be performed on the TS.

7.8.1 Adverse Events

AEs will be coded with the most recent version of MedDRA.

The analyses of AEs will be descriptive in nature. All analyses of AEs will be based on the number of subjects with AEs and not on the number of AEs.

For further details on summarization of AE data, please refer to "Analysis and Presentation of Adverse Event Data from Clinical Trials" ([7](#)) and "Handling of missing and incomplete AE dates" ([3](#)).

The analysis of AEs will be based on the concept of treatment emergent AEs. That means that all AEs will be assigned to screening or on-treatment phase as defined in [Section 6.1](#). AEs will be analysed based on actual treatments, as defined in [Table 6.1: 1](#).

An overall summary of AEs will be presented. This overall summary will comprise summary statistics for the class of AESIs.

CTP: *A potential severe Drug Induced Liver Injury (DILI) is considered an AESI in this trial. A potential severe Drug Induced Liver Injury (DILI) that requires follow-up is defined by the following alterations of hepatic laboratory parameters:*

- *An elevation of AST (aspartate transaminase) and/or ALT (alanine transaminase) ≥ 3 fold ULN combined with an elevation of total bilirubin ≥ 2 fold ULN measured in the same blood sample, or in samples drawn within 30 days of each other, or*
- *Aminotransferase (ALT, and/or AST) elevations ≥ 10 fold ULN*

The investigator had to classify on the eCRF whether an observed AE was an AESI or not.

According to ICH E3 ([8](#)), in addition to Deaths and Serious Adverse Events, ‘other significant’ AEs need to be listed in the clinical trial report. These will be any non-serious adverse event that led to an action taken with study drug (e.g. discontinuation or dose reduced or interrupted).

The frequency of subjects with AEs will be summarised by treatment, primary SOC and preferred term. AEs which were considered by the investigator to be drug related will be summarised separately. Separate tables will also be provided for subjects with SAEs and subjects with AESIs. AEs will also be summarized by maximum intensity.

The SOCs and preferred terms within SOCs will be sorted by descending frequency over all treatment groups.

For disclosure of AE data on ClinicalTrials.gov, the frequency of subjects with non-serious AEs occurring with an incidence of greater than 5 % (in preferred terms) will be summarised by treatment, primary SOC and preferred term. The frequency of subjects with SAEs will also be summarised.

For support of lay summaries, the frequency of subjects with drug-related SAEs will be summarized by treatment, primary SOC and preferred term.

7.8.2 Laboratory data

The analyses of laboratory data will be descriptive in nature and will be based on BI standards “Display and Analysis of Laboratory Data” ([9](#)).

Analyses will be based on normalised values, which means transforming to a standard unit and a standard reference range. The original values will be analysed if the transformation into standard unit is not possible for a parameter.

Descriptive statistics of laboratory values over time and for the difference from baseline (see [Section 6.7](#)) will be provided. Frequency tables of changes between baseline and last value on treatment with respect to the reference range will be presented.

Unscheduled measurements of laboratory data will be assumed to be repeat measurements of the most recent scheduled measurement (e.g. for follow-up or confirmation of a particular value). Therefore, unscheduled measurements will be assigned to the planned time point of the previous scheduled measurement. Descriptive statistics will be calculated by planned time point based on the worst value of the subject at that planned time point (or assigned to that planned time point).

Clinically significant abnormal laboratory values are only those identified either in the Investigator's comments or at the Report Planning Meeting at the latest. It is the Investigator's responsibility to decide whether a lab value is clinically significant abnormal or not.

Laboratory data will be compared to their reference ranges. Values outside the reference range as well as possibly clinically significant values will be highlighted in the listings. Possibly clinically significant laboratory values will be listed in Section 15.4.1.

Clinically relevant findings in laboratory data will be reported as baseline conditions (prior to start of administration of study treatment) or as AEs (after start of administration of study treatment) if judged clinically relevant by the investigator, and will be analyzed as such.

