## FLOW CHART - IV GROUP

Period	Visit	Day	Planned time (relative to first drug administration) [h:min]	Approximate clock time of actual day [h:min]	Event and comment	Safety laboratory	PK serum	12-lead ECG	Vital signs (BP, PR)	Questioning for AEs and concomitant therapy 	Query regarding local tolerability 
SCR	1	-21 to -3			Screening (SCR) 	x		x	x		
	2	-2	-48:00	8:00	Ambulatory visit	x 				x	
		-1	-14:00	18:00	Admission to trial site	x 				x	
		1	-3:00	06:00	Allocation to treatment 	x 	x 	x 	x 	x 	
			0:00	08:00	Drug administration start of infusion						
			0:30	08:30	end of infusion		x	x		x	x
			2:00	10:00	Light breakfast 		x	x	x		x
			4:00	12:00			x	x	x	x	
			8:00	16:00	Snack (voluntary) 		x	x	x		
			12:00	20:00			x	x	x	x	x
			24:00	08:00	Breakfast 	x	x	x	x	x	
			34:00	18:00	Dinner 		x		x	x	
			48:00	08:00	Breakfast  , discharge from trial site (confirmation of fitness) 		x	x	x	x	
		4	72:00	08:00	Ambulatory visit		x				x
		6	120:00	08:00	Ambulatory visit		x				x
		8	168:00	08:00	Ambulatory visit	x	x	x	x	x	
		11	240:00	08:00	Ambulatory visit		x				x
		14	312:00	08:00	Ambulatory visit	x	x	x	x	x	
		21	480:00	08:00	Ambulatory visit		x	x	x	x	
		28	648:00	08:00	Ambulatory visit	x	x	x	x	x	
		56	1320:00	08:00	Ambulatory visit	x	x	x	x	x	
FU	3	56 to 59			End of trial (EoTrial) examination 	x		x	x	x	x

1. Subject must be informed and written informed consent obtained prior to starting any screening procedures. Screening procedures include physical examination, check of vital signs, inclusive body temperature if it is still needed based on the status of pandemic, ECG, safety laboratory (including drug screening), demographics (including determination of body height and weight, smoking status and alcohol history), relevant medical history, concomitant therapy and review of inclusion/exclusion criteria.
2. The time is approximate; the procedure is to be performed and completed within the 3 h prior to drug administration.
3. If several actions are indicated at the same time, the intake of meals will be the last action.
4. At the end of trial visit the EoTrial examination includes physical examination, vital signs, ECG, safety laboratory, recording of AEs and concomitant therapies. EOT to be performed not before last PK sampling.

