## 1.2.4 Residual Effect Period

The Residual Effect Period (REP) is the period after the last dose with measurable drug levels and/or PD effects still likely to be present.

For BI 765080, a REP has not yet been determined. Conservatively, an observation period of 8 weeks has been selected, which is about 9-fold of the estimated t1/2 at 100 mg (approx. 6 days). Therefore, the individual subject's end of trial is on Day 56 to 59 following administration of investigational drug at the earliest (see [Flow Chart](#)).

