### **6.2.3 Follow-up period and trial completion**

For AE assessment, laboratory tests, recording of ECG and vital signs, and physical examination during the follow-up period, see Sections [5.2.2](#) to [5.2.5](#).

Subjects who discontinue treatment before the end of the planned treatment period should undergo the EoTrial Visit.

If needed in the opinion of the investigator, additional visits may be scheduled after the EoTrial Visit for continued safety monitoring.

All abnormal values (including laboratory parameters) that are assessed as clinically relevant by the investigator will be monitored using the appropriate tests until a return to a medically acceptable level is achieved. (S)AEs persisting after a subject's EoTrial Visit must be followed until they have resolved, have been sufficiently characterised, or no further information can be obtained.

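### The laboratory shift table uses only the Day 56–59 value, so it does not count subjects who leave the reference range during exposure and recover

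*SAP*

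**What the plan says.** SAP 7.8.2 specifies one categorical summary of laboratory change: "Frequency tables of changes between baseline and last value on treatment with respect to the reference range will be presented".

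Three other provisions fix what that means:

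- **On-treatment.** SAP 6.1 states: "Measurements will be considered on-treatment, if they were taken within the on-treatment phases as defined in Table 6.1: 1". In that table the phase begins when dosing starts and ends at "12:00 a.m. on day after last contact date". There is no cut-off tied to half-life or residual effect.
- **Baseline.** Under SAP 6.7, "baseline is defined as the last available value prior to start of infusion/injection".
- **Last contact.** Protocol 1.2.4 says that "the individual subject's end of trial is on Day 56 to 59 following administration of investigational drug at the earliest". Footnote 4 to both flow charts adds: "At the end of trial visit the EoTrial examination includes physical examination, vital signs, ECG, safety laboratory, recording of AEs and concomitant therapies". The flow charts also schedule a safety laboratory sample at Day 56 itself.

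SAP 7.8.2 plans other laboratory displays too: descriptive statistics by planned time point and for change from baseline, using each subject's worst value at that time point; listings that highlight out-of-range values; and a listing of possibly clinically significant values. Under SAP 7 the descriptive statistics include the minimum and maximum. Findings that the investigator judges clinically relevant after dosing become adverse events, which SAP 7.8.1 counts per subject.

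**The concern.** A baseline-to-last comparison is natural when dosing continues up to the last sample. Here there is a single dose, and the last sample is timed so that the drug should be essentially gone. Protocol 1.2.4 explains the timing: "Conservatively, an observation period of 8 weeks has been selected, which is about 9-fold of the estimated" half-life at 100 mg, which it puts at roughly 6 days.

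For completers, the values taken while drug is present therefore do not enter the shift table. If ALT, CK or CRP rises above range on Day 2, 8 or 14 and is back in range by Day 56, the subject appears as normal to normal. The table could look clean in both arms despite shifts during exposure.

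This matters somewhat more here because the earlier clinical experience described in Protocol 1.2.3 and 1.3 is intravenous, so this trial adds the subcutaneous route. With 14 subjects per arm, the number who crossed a limit is also a more natural summary than a mean.

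**Working it through.** **Inputs**

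- Half-life at 100 mg IV: geometric mean 137 h, gCV 29.0%, preliminary (Protocol Table 1.2.3: 1).
- Day 56 is planned at 1320 h (flow charts). Day 59 is three days later: 1320 + 72 = 1392 h.
- Earlier post-dose safety laboratory times, as the flow charts read in the available text: 24, 168, 312 and 648 h (IV); 24, 72, 144, 312 and 648 h (SC).

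**Step 1. The protocol's own figure.** 56 days / 6 days = 9.3, which agrees with its statement of about nine half-lives. With the unrounded half-life, 1344 h / 137 h = 9.8.

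**Step 2. Where each laboratory sample falls.** Number of half-lives = t / 137. Fraction remaining = 2^(−t/137), a mono-exponential approximation.

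| Time | Half-lives | Fraction remaining | In shift table for a completer? |
|---|---|---|---|
| 24 h (Day 2) | 0.18 | 89% | no |
| 72 h (Day 4, SC) | 0.53 | 69% | no |
| 144 h (Day 7, SC) | 1.05 | 48% | no |
| 168 h (Day 8, IV) | 1.23 | 43% | no |
| 312 h (Day 14) | 2.28 | 21% | no |
| 648 h (Day 28) | 4.73 | 3.8% | no |
| 1320 h (Day 56) | 9.64 | 0.13% | the last value is taken |
| 1392 h (Day 59) | 10.16 | 0.09% | within Day 56–59 |

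**Step 3. Sensitivity to the half-life.** Assume log-normal half-lives with gCV 29%: σ = √ln(1 + 0.29²) = 0.284. The approximate 95% range is 137 × exp(±1.96 × 0.284) = 79 to 239 h. Day 56 then falls at 16.8 to 5.5 half-lives. Even at the slow end, the table reads a late sample and passes over those from Days 2 to 14.

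**Step 4. What the alternative costs in chance findings.** Assume that 2.5% of healthy values lie above the upper limit. One sample gives a 2.5% chance of a high value. Six independent samples give 1 − 0.975⁶ = 14.1%. For 14 subjects that is 14 × 0.025 = 0.35 against 14 × 0.141 = 2.0 expected subjects per parameter. Repeat samples from one person are correlated, so 14% is an upper-end figure.

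**The case against.** The strongest reply is that the shift table is one display among several, and the others show what it omits. A single extreme value appears as the maximum or minimum at its time point, and the worst value per subject is used there. Every out-of-range value is highlighted in a listing, and 14 subjects per arm can be read one by one. Clinically relevant changes are counted as adverse events, and liver changes meeting the DILI criteria are adverse events of special interest with their own table. All of this stands, and it confines the point to the shift table.

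Three stronger readings are tempting, but the documents do not support them:

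- **That the laboratory analysis as a whole hides transient effects.** It does not, for the reasons just given.
- **That this is the only planned count of subjects crossing the reference range.** The SAP text states no other, but it refers to a sponsor laboratory standard that is not available here and may add tables.
- **That last values will be normal by rule.** Protocol 6.2.3 says that clinically relevant abnormal values "will be monitored using the appropriate tests until a return to a medically acceptable level is achieved". This requires continued monitoring. It does not make the scheduled end-of-trial value normal, and it does not cover mild out-of-range values.

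It is also fair to say that laboratory tests are further safety parameters, neither primary nor secondary endpoints, in a descriptive trial. No bioavailability conclusion depends on this table. The chance-shift cost in Step 4 is real too, across dozens of parameters and with no placebo arm for comparison.

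**Conclusion.** The point holds for the shift table alone. For every completer it compares baseline with a sample taken 9.6 to 10.2 half-lives after the single dose. It therefore describes end-of-trial status and does not count subjects who leave the reference range between about Day 2 and Day 28 and recover. The remaining gap is narrow: the SAP text states no per-subject count of transient shifts that were not judged clinically relevant.

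The half-life multiple rests on a preliminary IV geometric mean; applying it to the SC arm is an assumption. The main conclusion does not depend on it, because a last-value rule drops any shift that has resolved by the end of the trial, whatever the half-life. Subjects who discontinue early have an earlier last value. The weight is minor: a cheap improvement to descriptive safety reporting.

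**What to change.** In SAP 7.8.2, add for each laboratory parameter a table of baseline category (low, normal, high) against the category of the subject's lowest on-treatment value, and another against the highest. Alternatively, give the shift table by planned visit. Keep baseline-to-last, labelled as an end-of-trial recovery table. Taking each subject's extreme over the phase extends the worst-value approach that the SAP already uses within a time point.

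The cost is a change of SAP wording and some standard output, with no new data. If extremes are used, a footnote should say that about six samples per subject raise the rate of chance shifts (up to about 14% against 2.5% per parameter for a 2.5% tail, if samples were independent) and that there is no placebo arm to calibrate them. The by-visit version avoids that inflation within each table, but a subject may then appear at more than one visit.
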